#### Assessment of Association

The association assessment categories that will be used for this study are:

- Associated – The event is temporally related to the administration of the study product and no other etiology explains the event.
- Not Associated – The event is temporally independent of the study product and/or the event appears to be explained by another etiology.

The investigator must provide an assessment of association or relationship of AEs to the study product based on:

- Temporal relationship of the event to the administration of study product;
- Whether an alternative etiology has been identified;
- Biological plausibility;
- Existing therapy and/or concomitant medications.

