### **Primary Safety Endpoints:**

1. Rapid deterioration of respiratory or clinical status on transfusion of SARS-CoV-2 convalescent plasma due to presumed antibody dependent enhancement or other mechanisms. Since patients in this study are already in respiratory distress, further worsening of respiratory status will be defined as below and causes attributed by treating physician. Any escalation of oxygenation or ventilatory needs within the 12 hours after plasma infusion will be considered as a deterioration. This includes new requirement for supplemental oxygen in a person not on oxygen, an increase of >25% in FiO2; need for non invasive or invasive mechanical ventilation in subjects not requiring these at the time of infusion. In patients already on mechanical ventilation, an increase in PEEP and or FiO2 of >25% will also be considered a respiratory deterioration.
2. Cumulative incidence of all serious adverse events attributed to plasma therapy during the study period: transfusion reaction (fever, rash), transfusion related acute lung injury (TRALI), transfusion associated circulatory overload (TACO), transfusion related infection

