### **11.2.2 Unanticipated Problem Involving Risk to Subject or Other (UPIRSO)**

The Office for Human Research Protections (OHRP) considers unanticipated problems involving risks to participants or others to include, in general, any incident, experience, or outcome that meets all of the following criteria:

- Unexpected in terms of nature, severity, or frequency given (a) the research procedures that are described in the protocol-related documents, such as the Institutional Review Board (sIRB)-approved research protocol and informed consent document; and (b) the characteristics of the participant population being studied.
- Related or possibly related to participation in the research (“possibly related” means there is a reasonable possibility that the incident, experience, or outcome may have been caused by the procedures involved in the research).
- Suggests that the research places participants or others at a greater risk of harm (including physical, psychological, economic, or social harm) than was previously known or recognized.

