## 12.2 Halting Criteria for the Study

The study enrollment and dosing will be stopped, and an ad hoc review will be performed if any of the specific following events occur or, if in the judgment of the study physician or the ISM, subject safety is at risk of being compromised:

1. Death within one hour of plasma infusion
2. Occurrence of a life-threatening allergic/hypersensitivity reaction (anaphylaxis), manifested by bronchospasm with or without urticaria or angioedema requiring hemodynamic support with pressor medications or mechanical ventilation, TRALI, TACO.
3. One subject with an SAE specifically associated with study product.
4. Two subjects with a Grade 3 or higher lab toxicity for the same parameter associated with study product.
5. An overall pattern of symptomatic, clinical, or laboratory events that the medical monitor, ISM, or IRB consider associated with study product and that may appear minor in terms of individual events but that collectively may represent a serious potential concern for safety.

6. Any other event(s) which is considered to be a serious adverse event related to the study infusion in the good clinical judgment of the responsible physician and or ISM. These will be appropriately documented.

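### The two-category attribution rule biases the attributed-SAE primary safety endpoint downward, chiefly for respiratory and circulatory events, by an amount the documents do not let us compute

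*Combined protocol and SAP*

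**What the plan says.** The Assessment of Association text in Section 11.3 gives two categories. An event is associated if "The event is temporally related to the administration of the study product and no other etiology explains the event". It is not associated if "The event is temporally independent of the study product and/or the event appears to be explained by another etiology". The investigator weighs timing, any identified alternative cause, biological plausibility and other therapy, but there is no possible or probable category.

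Section 4.1 defines the second primary safety endpoint as "Cumulative incidence of all serious adverse events attributed to plasma therapy during the study period". It names transfusion reaction (fever, rash), TRALI, TACO and transfusion-related infection. It gives no attribution rule of its own. The Section 11.3 scale is the only one in the document, so I read attributed as associated on that scale.

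On the population, Section 4.1 remarks: "Since patients in this study are already in respiratory distress". Its first primary safety endpoint is defined by what happens and not by cause: "Any escalation of oxygenation or ventilatory needs within the 12 hours after plasma infusion will be considered as a deterioration". The treating physician then records a cause.

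Other sections use other terms for relatedness:
- Section 11.2.1 speaks of suspected relationships.
- Section 11.2.2 uses "Related or possibly related to participation in the research".
- Section 12.2 uses associated in halting criteria 3, 4 and 5 (criterion 3 reads "One subject with an SAE specifically associated with study product") and related in criterion 6.

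**The concern.** The scale works by exclusion. A serious event soon after infusion leaves the endpoint once another cause appears to explain it. In this population such a cause is often at hand for the events that matter most. TRALI, TACO and antibody-dependent enhancement show themselves as respiratory or circulatory worsening, and so does COVID-19 pneumonia. Other treatments and co-enrolment in other trials are allowed, which adds further candidate explanations.

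At stake is how a low attributed-SAE rate is read. The trial is open label and single arm, and the on-site investigator assigns causality. A low count could mean that plasma is safe, or that ambiguous events were classed out. The endpoint alone cannot show which.

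**Working it through.** **Step 1. Follow one event through the rule.** Take an SAE that plasma caused, hours after infusion, in a patient whose pneumonia could account for it.
- The timing condition for associated is met. The condition that nothing else explains the event is not met if the investigator judges that COVID-19 explains it.
- The not-associated category is joined by and/or, so "the event appears to be explained by another etiology" is enough on its own, despite the close timing.
- With no middle category, the event drops out of the endpoint even though the plan was followed exactly.

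**Step 2. Which events are exposed.** Every qualifying feature under inclusion criterion 3 (Section 5.1) is respiratory, and patients ventilated for up to 14 days are not excluded. TRALI, TACO and ADE-like worsening therefore overlap with the baseline illness, and fever does too. Rash and transfusion-related infection are not readily explained by COVID-19 pneumonia and are less affected.

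**Step 3. Direction and possible size.** The plan gives no expected SAE rate, threshold or power for this endpoint, so there is no figure to reproduce. The inputs are:
- N = 41 (Cohort 1), 90 (Cohort 2), 131 (total), from Section 7.
- t, the true proportion with a plasma-caused SAE: assumed 3% to 10%.
- q, the share of those SAEs judged to have another explanation: assumed 0 to 0.9.

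If false attributions are negligible, the expected attributed count is N × t × (1 − q), and the chance of reporting none is (1 − t(1 − q))^N.

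With t = 5%, the true expected count in 131 patients is 131 × 0.05 = 6.55.

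| q | Expected attributed, N = 131 | P(none), N = 131 | P(none), N = 90 | P(none), N = 41 |
|---|---|---|---|---|
| 0 | 6.55 | 0.001 | 0.010 | 0.122 |
| 0.5 | 3.28 | 0.036 | 0.102 | 0.354 |
| 0.75 | 1.64 | 0.192 | 0.322 | 0.597 |
| 0.9 | 0.655 | 0.519 | 0.637 | 0.814 |

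For N = 131, P(none) at q = 0.5 runs from 0.138 (t = 3%) to 0.001 (t = 10%). At q = 0.9 it runs from 0.675 to 0.268.

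**Step 4. What the exact interval would show.** The Clopper-Pearson 95% upper limit for 0 of N is 1 − 0.025^(1/N): 8.6% for 41, 4.0% for 90 and 2.8% for 131. These limits cover sampling error in t(1 − q), not in t. If the truth were 5%, a count of zero in Cohort 2 or overall would give an interval that excludes it.

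**Step 5. Does anything elsewhere correct the endpoint?**
- Section 7.1 presents the proportions with any SAE and with any Grade 3 or higher event, with no attribution filter. They are not limited to the listed event types or to an early period. Death and prolonged hospitalization count as SAEs, so background disease will weigh heavily, and there is no control arm.
- Section 11.2.1 collects SAEs regardless of suspected cause through 30 days. This supplies data but does not change the endpoint.
- Under Section 12.1 the Independent Safety Monitor (ISM) reviews each SAE and writes an assessment. No rule says that this can reclassify an event.
- The first primary safety endpoint does not depend on cause, but it covers only respiratory escalation within 12 hours.
- Halting criteria 1 and 2 name death within an hour, anaphylaxis, TRALI and TACO without the word associated. They bear on trial conduct, not on the reported rate.

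**The case against.** The strongest reply is that the scale asks for judgment. It asks whether another cause explains the event or appears to, and whether one has been identified. It does not say that having COVID-19 is itself an explanation. TRALI and TACO are specific diagnoses, and transfusion-related events also go to the blood bank for investigation (Section 11.2.1). Section 11.2.2 repeats a regulatory definition used as a reporting trigger, so a different threshold there is not in itself a contradiction. The safeguards in Step 5 also mean that overall safety does not rest on attribution alone.

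Much of this stands. A reader might infer that COVID-19 will almost always explain the event, that the endpoint is driven to zero, and that a clean safety result would be an artefact of the definition. The documents do not support that. They give no value for q, some listed events are little affected, and P(none) in 131 patients passes one half only near q = 0.9 at t = 5%. With q = 0.5 about three attributed events would still be expected.

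What does not stand is the idea that the safeguards repair this endpoint. None of them changes which SAEs it counts, and judgment has no category in which to record an uncertain case.

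**Conclusion.** The second primary safety endpoint is biased downward, chiefly for respiratory and circulatory SAEs. This follows from the wording of the scale and from the population. It assumes that attributed means associated under Section 11.3, that at least some plasma-caused SAEs have a competing explanation (q > 0), and that false attributions are negligible. The size cannot be computed from the documents; the figures above illustrate a range under assumed t and q. The effect on the overall safety assessment is limited by the unfiltered summaries, causality-free SAE collection to 30 days, ISM review, the 12-hour endpoint and halting criteria 1 and 2. The point is a cheap improvement to how one primary safety endpoint is reported. It does not show that the trial's safety monitoring fails.

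**What to change.** 1. Beside the attributed rate, report for each cohort the proportion with any SAE of the listed types, or any respiratory or circulatory SAE, in a pre-specified early window after infusion regardless of attribution. Use Clopper-Pearson intervals, which Section 7 already adopts. The 12-hour window of Section 4.1 and a second window through day 4 would serve as examples.
2. Add a possibly-associated category to the causality item, and show the second primary safety endpoint with and without it. Showing both avoids having to decide in advance that every possible case counts as attributed.
3. The wording in Sections 11.2.1 (suspected), 11.2.2 (possibly related), 11.3 (associated) and 12.2 (associated in criteria 3, 4 and 5; related in criterion 6) must be reconciled by the safety team. A new category would touch the halting criteria through the shared word. No halting rule is proposed here.

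The cost is one CRF category and one extra table. Sample size and the efficacy rules do not change. The early-window table should need no new data: Section 8 records infusion start and end times, and Section 11.2.3 lists time of onset. That section concerns non-serious events, so confirm that the SAE form carries onset time too. The downside is that the broader rate will include disease-related events that a single-arm trial cannot separate from plasma effects, so the two rates should be read together.

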## 12. Safety Oversight

## 12.1 Monitoring Plan

1. All AEs and SAEs will be reviewed by protocol team.
2. An Independent Safety Monitor (ISM) will be appointed. The ISM is a physician with expertise in infectious diseases and whose primary responsibility is to provide timely independent safety monitoring. An ISM has the authority to readily access study participant records. The ISM reviews any SAE that occurs at the study site in real time and provides a written assessment. **[name], Chief, Division of Infectious Diseases, Medical College of Wisconsin** will serve in this role.

### Study monitoring

- a. As per ICH-GCP 5.18 and FDA 21 CFR 312.50, clinical protocols are required to be adequately monitored by the study sponsor.
- b. Informed consent process documents for each subject needs to be available.
- c. There is compliance with recording requirements for data points
- d. All SAEs are reported as required
- e. Individual subjects' study records and source documents align
- f. Investigators are in compliance with the protocol.
- g. Regulatory requirements as per Office for Human Research Protections-OHRP), FDA, and applicable guidelines (ICH-GCP) are being followed.

## 12.2 Halting Criteria for the Study

The study enrollment and dosing will be stopped, and an ad hoc review will be performed if any of the specific following events occur or, if in the judgment of the study physician or the ISM, subject safety is at risk of being compromised:

1. Death within one hour of plasma infusion
2. Occurrence of a life-threatening allergic/hypersensitivity reaction (anaphylaxis), manifested by bronchospasm with or without urticaria or angioedema requiring hemodynamic support with pressor medications or mechanical ventilation, TRALI, TACO.
3. One subject with an SAE specifically associated with study product.
4. Two subjects with a Grade 3 or higher lab toxicity for the same parameter associated with study product.
5. An overall pattern of symptomatic, clinical, or laboratory events that the medical monitor, ISM, or IRB consider associated with study product and that may appear minor in terms of individual events but that collectively may represent a serious potential concern for safety.

6. Any other event(s) which is considered to be a serious adverse event related to the study infusion in the good clinical judgment of the responsible physician and or ISM. These will be appropriately documented.

## **Halting Criteria/Rules for Subject Infusion**

Infusion of study drug will be halted **in a study subject** if any of the following manifestations of anaphylaxis develop and will not be restarted:

- Skin or mucous membrane manifestations: hives, pruritus, flushing, swollen lips, tongue or uvula that do not respond to standard therapy with anti-allergic and steroid medications
- Respiratory compromise: New onset wheezing, stridor, hypoxemia related to infusion
- Any other symptom or sign which in the good clinical judgment of the study clinician or supervising physician warrants halting the infusion. For example, manifestations of anaphylaxis and may warrant an immediate halt prior to meeting full SAE criteria

## **13. Ethics/Protection of human subjects**

### **13.1 Ethical Standard**

We will ensure that the legal and ethical obligations associated with the conduct of clinical research involving human subjects are met.

As the Department of Health and Human Services continues to strengthen procedures for human subjects' protections via new regulations, MCW will review these evolving standards in relation to the proposed activities and will advise the investigators on those that may apply.

MCW has a Federal wide Assurance (FWA) number on file with the Office for Human Research Protections (OHRP).

This assurance commits a research facility to conduct all human subjects' research in accordance with the ethical principles in The Belmont Report and any other ethical standards recognized by OHRP. Finally, per OHRP regulations, the research facility will ensure that the mandatory renewal of this assurance occurs at the times specified in the regulations.

### **13.2 Institutional Review Board**

MCW IRB will review this protocol and all protocol-related documents and procedures as required by OHRP and local requirements before subject enrollment. MCW IRB currently holds and will maintain a US FWA issued by OHRP for the entirety of this study.

### **13.3 Informed Consent Process**

The informed consent process will be initiated before a potential subject or their HCPOA agrees to participate in the study and should continue throughout the individual's study participation. The subject or HCPOA will be consented before any procedures are undertaken for the study. The process for consent will be documented in the research records.

Two alternative consent methods will be available for this study:

1. Electronically: transmitting a consent form via email, obtaining e-consent utilizing an iPad, or utilizing a cloud-based system for delivery and communicating in-person with subjects or HCPOA.
2. Phone Call or Video Conference: Example – this method could include utilizing the phone in the subject's room or utilizing video conferencing services such as WebEx, Skype, etc to connect with patient and or HCPOA.

Regardless of the method utilized, a consent form will be provided to the subject either in person by health care staff or electronically.

If consent cannot be obtained electronically or in person, it is required that an impartial witness will be present (via phone or teleconference).

When a witness is being utilized, the following must occur:

1. The witness must be present for the entire consent discussion and confirm that the potential subject's questions have been answered.
2. The investigator must confirm that the potential subject is willing to participate and sign the consent form with the witness present (via phone or teleconference).
3. The potential subject must confirm that he or she wishes to participate and has signed and dated the consent form.

#### Documenting Informed Consent

##### 1. Electronically

Example – The consent form can be signed, scanned, and sent via email or fax from the subject to the team. In addition, electronic signatures can be utilized.

##### 2. Photograph

Example – The subject or research team can photograph the entire signed consent form by camera, cellular phone, etc. and send the picture to the research team. The picture can be taken from outside of the isolation area as long as the signed consent form can be seen clearly.

##### 3. Confirmation

Example – The impartial witness present for the consenting process can attest that the subject confirmed the he/she wished to participate in the project and signed the consent form.

The method of obtaining informed consent should be included in study records along with the signed consent form (if available). If a signed consent form is not available for the reasons outlined in this document, the study record should include an explanation of which method was used for confirming that the subject signed the consent form as well as the explanation of why the originally signed consent form could not be filed.

An electronic copy of the signed informed consent document will be available to the subject for their records. The consent will explain that subjects may withdraw consent at any time throughout the course of the trial. Extensive explanation and discussion of risks and possible benefits of this investigation will be provided to the subjects in understandable language. Adequate time will be provided to ensure that the subject has time to consider and discuss participation in the protocol.

The consent will describe in detail the study interventions/products/procedures and risks/benefits associated with participation in the study. The rights and welfare of the subjects will be protected by emphasizing that their access to and the quality of medical care will not be adversely affected if they decline to participate in this study.

### **13.4 Subject Confidentiality**

Subject confidentiality is strictly held in trust by the participating investigators, their staff, and the sponsors and their agents. No information concerning the study, or the data will be released to any unauthorized third party without prior written approval of the sponsor. The results of the research study may be published, but subjects' names or identifiers will not be revealed. Records will remain confidential. To maintain confidentiality, the PI will be responsible for keeping records in a locked area and results of tests coded to prevent association with subjects' names. Data entered into computerized files will be accessible only by authorized personnel directly involved with the study and will be coded. Subjects' records will be available to the FDA, the NIH, the manufacturer of the study product and their representatives, investigators at the site involved with the study, and the IRB.

### **14. Research Sample Disposition:**

Research samples will be drawn from enrolled patients throughout the course of their hospitalization to investigate the early immune response and the impact of treatment. In coordination with these studies, the development of the adaptive, or immune memory response will be investigated. These samples will be drawn in coordination with clinical labs and the blood volume will be limited to 30 ml. These blood samples will be processed and studied at the Versiti Blood Research Institute in the labs of Drs. [name], [name], [name], [name], [name], [name], and [name]. [name] as lab investigator will be in overall control of sample security and distribution to other investigators named above. Immunologic and hemostatic assays will be performed on these samples in compliance with Medical College of Wisconsin safety guidelines. Research assays will include in vitro studies of lymphocyte and antibody development, mediators of the immune response particularly circulating cytokines, hemostasis, and platelet function.

Blood samples will be obtained per Table 1 and appendix 2. This will consist of 20ml citrate (blue-topped) and 10ml EDTA (purple-topped) tubes. If the collected blood volume is limited by clinical condition, sample collection will be limited to 10ml citrate and 10ml EDTA initially, then a 10ml citrate tube. Blood samples will be de-identified with only study ID# (refer to section 8), and date/time of collection. These samples will be processed at Versiti Blood Research Institute to obtain platelet-poor plasma (PPP), platelet-rich plasma (PRP), and enriched platelet and peripheral blood mononuclear cell (PBMC) samples. Samples will then be analyzed. Residual de-identified sample will be stored for batched analyses at -70C or in liquid nitrogen.

Proposed research activities will take place in the laboratories at the Versiti Blood Research Institute. Once collected, samples will be shipped deidentified to the Versiti BRI and received by [name] or designee and processed further for research tests as indicated above. Collection, storage, and communication of research samples will be conducted in a manner that is compliant with HIPAA regulations.

Refer to appendix 2 for further collection and shipping instructions.

